Risks. The risk of potential coercion is judged to be minimal.

Minimization. The risk of coercion will be minimized by following standard procedures for obtaining informed consent. We will fully explain the study procedures, risks, benefits, and alternatives to all patients. Also, patients who do not consent or who withdraw at any time will receive usual clinical treatment with no prejudice. Additionally, participant remuneration will be set at modest monetary levels as used in similar studies, including our pilot work. We will obtain permission from the patient's treating physician to ensure that approaching the patient for research participation is clinically appropriate.

Risk of clinical deterioration/suicidality

Risks. In this type of population, the risk of clinical deterioration is present.

Minimization. Clinical deterioration, including suicidality will be monitored in multiple ways. 1) During in person interviews, study staff will assess for suicide risk, symptoms, and clinical deterioration and take appropriate action if needed. 2) The mobile app will contain questions regarding suicide risk and psychotic symptoms in every session, and will prompt participants to contact a crisis hotline, 911, and/or their local treatment provider/hospital if such risk is reported for immediate assistance. 3) Mobile device data will be uploaded onto secure servers remotely. As real-time data review is not feasible or sustainable in typical clinical settings, mobile data will be reviewed weekly by the study clinician as part of his/her routine monitoring and report-writing duties. This type of strategy is known as asynchronous communication (where there is a gap between communications compared with synchronous or "live" communication) and is often

Date most recently revised (02/15/19)

Protocol Version 1.2

Page 9 of 18

adopted in mobile health research. Patients will be informed that their responses will be reviewed periodically (not in real time), and that they may be contacted by study staff if safety risk is detected for the purposes of providing further assessment and assistance as necessary.

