[name] will be responsible for overseeing the daily safety of all participants. There are several ways in which they will become aware of adverse events. First, research staff will ask patients about serious adverse events (as defined by Office of Human Research Protections (OHRP); e.g., inpatient hospitalization). Second, all study staff will be trained in the OHRP definitions of adverse events that are also unanticipated problems; serious adverse events; or unanticipated problems that are not adverse events. All study staff are required to report any event that might meet one of these criteria to one of the PIs immediately both verbally and in writing. Any report of a serious adverse event will result in one of the PIs contacting the participant to further assess the event.

Adverse Events Definitions

Adverse Event – any unfavorable and unintended sign, symptom or disease temporally associated with the use of a medical or behavioral treatment or intervention regardless of whether it is considered related to the treatment or intervention.

Expected Adverse Event – an event that may be reasonably anticipated to occur as a result of the study procedure and is described in the consent form.

Unexpected Adverse Event – any adverse event which is not described in the consent form and is unanticipated. An event that might have been anticipated but is more serious than expected or occurs more frequently than expected, would be considered an unexpected adverse event.

Serious Adverse Event - (21 CFR 312) include any untoward medical occurrence that at any dose results in death or the immediate risk of death, hospitalization or prolonging of an existing hospitalization, persistent or significant disability/incapacity or a congenital anomaly/birth defect (NIH guide-6/11/99).

Study Definitions

Specifically, we will consider the following events Serious Adverse Events (SAE):

- a. Death for any reason;
- b. A suicide attempt, defined as any action taken with intent to die, as stated by the patient or noted in the medical record;
- c. Inpatient psychiatric hospitalization

Additionally, we will consider the following events non-serious Adverse Event (AE):

- a. Evidence of coercion to participate;
- b. Participant distress resulting in stopping of the assessment or intervention;
- c. Access of confidential information by a non-authorized person.

Severity

Each adverse event will be graded in terms of severity:

- a. Non-severe adverse event

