Both MPIs and the DSMB Chair will develop the Data Safety Monitoring Plan. It will then be circulated to the rest of the DSMB for feedback and approval. The board members will review the initial DSMB protocol to ensure that it captures the information necessary to evaluate the safety and efficacy of the study. The DSMB will then receive DSM reports bi-annually. A DSM report will include concerns about significant safety and data monitoring issues such as recruitment, retention, and quality of data collected.

Operating procedures of the DSMB include monitoring the protocol to evaluate the safety of the participants as pre-specified in the DSMP of the protocol, monitoring efficacy of the intervention being tested, and evaluating performance of the trial, as well as study admission data and protocol compliance. The specific content of the reports to the DSM include information about AEs and/or SAEs, treatment retention, recruitment, reasons for dropout, and interim efficacy data.

Only reports that meet the criteria of being a death (within 5 calendar days) or unexpected and related to study procedures (within 10 calendar days) will be reported to the DSMB within the specified timeframe after learning of the event. Summary reports of all adverse events will be provided to DSMB in bi-annual reports. Finally, as part of the annual progress report (noncompeting continuation application) to NIH, we would provide summary information on all adverse events that have occurred during that year.

As they deem necessary, the members of the DSMB will evaluate whether the presence of early unanticipated therapeutic results, side effects or adverse consequences are significant enough to warrant amendment, suspension, or early termination of the study and will independently make recommendations to the PIs to continue, to amend or to terminate the trial. Recommendations related to the study will be made in a written DSMB Report by the Board's Chairperson to the Principal Investigator and this DSMB Report, along with the DSMB meeting minutes, will be sent to the NIH Project Officer for the study.

E. Potential Benefits

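### The adverse-event inquiry covers only serious events, so non-serious app-related distress that does not stop use has no defined route into the promised summaries of all adverse events

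*Combined protocol and SAP*

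**What the plan says.** Section D3, item 2 (Safety Plan and Adverse Event Identification and reporting) states: "There are several ways in which they will become aware of adverse events". It then describes two. First, "research staff will ask patients about serious adverse events". Second, staff are trained in the regulatory definitions, and "All study staff are required to report any event that might meet one of these criteria to one of the PIs immediately". The criteria cover three classes: serious adverse events, unanticipated problems that are also adverse events, and unanticipated problems of other kinds.

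Under Adverse Events Definitions, an adverse event is "any unfavorable and unintended sign, symptom or disease temporally associated with the use of a medical or behavioral treatment or intervention", whether or not it is related. Study Definitions then names three non-serious adverse events: coercion, "Participant distress resulting in stopping of the assessment or intervention", and unauthorised access to confidential information. Under Attribution, each adverse event is placed on a five-level scale of relatedness to the intervention. Adverse Event Reporting requires an IRB form for each event, with severity and attribution.

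On what goes out, section D3, item 3 (DSMB) says: "Summary reports of all adverse events will be provided to DSMB in bi-annual reports". The same item, and section D1 under Risk of adverse events, promise NIH an annual summary that also covers all adverse events.

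On clinical state, section D1 (Risk of clinical deterioration/suicidality) says: "During in person interviews, study staff will assess for suicide risk, symptoms, and clinical deterioration and take appropriate action if needed". It adds: "The mobile app will contain questions regarding suicide risk and psychotic symptoms in every session". App data are reviewed weekly, and Table 1 schedules the BPRS at baseline and months 1, 2 and 4.

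**The concern.** The definition and the promised summaries are broad, but the means of finding events is narrow. A patient who finds the repeated questioning upsetting, or believes an exercise made the voices worse, but carries on using the app, has an adverse event under the general definition. No one is instructed to ask about it, and staff who hear of it must report it only if it qualifies as serious or as an unanticipated problem.

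This matters because of what the study is for. Recently hospitalised patients are prompted three times daily in month 1 and once daily in months 2 to 4, with suicide and psychosis items in every session. Tolerability of that schedule is part of what a feasibility study should pass on to the next trial. With one arm there is no control group to show an excess of distress, so information about cause has to come from the patient or from a clinician's judgement at the time.

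**Working it through.** No arithmetic applies: the plan states no adverse-event rate, and the point concerns ascertainment. The check is to follow types of event through the steps the protocol describes.

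| Event | Elicited? | Stated rule that brings it into the adverse-event record? |
|---|---|---|
| Psychiatric rehospitalisation | Yes, asked as a serious event | Yes: serious list, staff duty and reporting timelines |
| Distress that stops an assessment or the intervention | Not asked, but staff can see it when an in-person assessment stops | Yes: on the three-item non-serious list |
| BPRS psychotic item above 5 | Yes, by BPRS | Not explicit: clinical action, then a pointer to the reporting procedures |
| Worsening short of that level | Yes, by BPRS and app items | None |
| App-related distress that does not stop use | Cause not asked | None, unless it comes to notice and is judged an unanticipated problem |

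1. **Patient inquiry.** The only adverse-event question described concerns serious events. Table 1 lists no inquiry into harm caused by the app or the assessments. The End of Treatment Interview (months 1 and 4) invites likes and dislikes about the app and about taking part; no link from it to the adverse-event log is stated.

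2. **Staff duty.** A non-serious event that is not an unanticipated problem meets none of the three criteria. It can therefore be known to staff and still fall outside the duty.

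3. **Classification.** Under Adverse Event Reporting, the investigators sort events into three classes that closely follow the staff criteria; the first is further limited to problems related to study procedures or the intervention. An ordinary non-serious adverse event has no class here either.

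4. **From elicited worsening to the log.** The BPRS trigger in section D1 governs clinical action. It ends with a cross-reference to the reporting procedures, and those contain no rule for turning a BPRS rating or an app response into a logged event.

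5. **Attribution.** The five-level scale needs a view on whether the intervention caused the event. BPRS and app items measure how severe symptoms are, and no scheduled item asks about cause.

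6. **Output.** The summaries to the DSMB and NIH are to cover all adverse events. The last row of the table meets the general definition but has no reliable path to them; the row above it is measured but has no logging rule.

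**The case against.** The strongest reply is that this population is closely watched. Suicidality and psychotic symptoms are asked about in every app session, the app also covers affect, staff review the data weekly, and in-person assessment and the BPRS recur at months 1, 2 and 4. A reader might infer from the serious-only question that symptom worsening counts only if the patient volunteers it. The documents do not support that: worsening is elicited repeatedly, and distress that stops an assessment is a listed event that staff can observe. This part of the reply stands and confines the point to attribution, logging and distress that does not stop use.

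Three further replies have some force:

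- The reporting procedure speaks of staff who observe or are told of an adverse event contacting the investigators, which sounds wider than the three criteria. But it is activated by the serious events, disclosure and coercion named just before it, or by other unanticipated events, and it still depends on someone noticing or telling.
- The three-item list is not said to be exhaustive. That leaves the general definition in force, which makes the mismatch with the staff duty sharper.
- The Data Safety Monitoring Plan is still to be developed with the DSMB Chair, and the consent form is not among the pages available here. Either might contain a suitable inquiry; the protocol does not say so.

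A reader might also infer that the plan builds in a near-zero harm count that props up the minimal-risk statement. That goes too far. Sections E and F make that statement prospectively and cite no count, and the development outcomes given as examples in section C4 do not include adverse events.

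**Conclusion.** The point holds in limited form and should be acted on. As written, the protocol has no defined route for non-serious app-related distress that does not stop use, and no rule for when elicited worsening becomes an adverse event. Its broad definition, three-item list and staff reporting criteria do not match one another or the promised summaries. Followed literally, the plan under-counts non-serious harm in the reports it commits to.

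The under-count cannot be sized. If no events were reported in 20 patients, the one-sided exact 95% upper limit would be 1 − 0.05^(1/20) = 13.9%, but that follows from the sample size under any method of asking and does not measure this defect. Scaling it up would need the share of such events that patients volunteer, which the documents do not give.

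The verdict assumes that no separate document, such as the monitoring plan still to be written, already supplies the inquiry and the logging rule.

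**What to change.** Amend section D3, item 2:

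1. At the existing month 1, 2 and 4 visits, ask every patient a standard question on non-serious adverse events, including whether the app or the assessments caused distress or made symptoms worse.
2. Report solicited and volunteered events separately in the DSMB and NIH summaries.
3. State how BPRS ratings and app responses feed the adverse-event log, so that the cross-reference in section D1 leads to an actual rule. The content of that rule is for the sponsor to set.
4. Reconcile the general definition, the three-item non-serious list and the staff reporting criteria with one another, with Adverse Event Reporting, and with the summaries promised in section D1 and in D3, item 3.

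No new visits are needed. The cost is a few minutes at each of three visits for 20 patients, plus the extra events to log. That second part is not trivial: the definition applies regardless of relatedness, and each event needs the IRB form with severity and attribution. An open question in recently discharged patients could generate many such forms, so the sponsor should weigh that workload when reconciling the definitions.

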Adverse Event Reporting. Based on the sources of information detailed above as well as direct patient contact and/or consultation with the scientific team, [name] will determine if the event is: a) an adverse event that is also an unanticipated problem related to study procedures or intervention; b) a serious adverse event; or c) an unanticipated problem that is not an adverse event. Considering the nature of the study and sample, we expect serious adverse events to occur, including suicide attempts and rehospitalizations (e.g., due to relapse). However, given the nature of the study, it is unlikely that SAEs will be related to the study procedures. The other adverse events that are possible include: inadvertent disclosure of protected health information and coercion. If any of these adverse events occur, or any other unanticipated events that are identified, the following procedure will be activated:

The research staff member who observes or is notified of an adverse event will contact the MPIs or their designee immediately. The MPIs or their designee will complete a Butler Hospital IRB Adverse Event Form for each event that will include a level of severity and determine attribution (intervention-related or not). Reporting timeframes will vary by SAE type;

- 1) **expected and unrelated SAEs:** reviewed by the MPIs and reported to Butler IRB within 14 days ascertainment; provided to the DSMB in bi-annual data reports;
- 2) **unexpected or related SAEs:** to Butler IRB and DSMB within 10 days of ascertainment;
- 3) **all deaths:** to Butler IRB and DSMB within 5 days of ascertainment.

3. Data and Safety Monitoring Board (DSMB)

The DSMB will be constituted and will be responsible for monitoring the safety of participants and the quality of the data, as well as deciding on the appropriate termination of the study either when significant benefits or

risks have been uncovered or when it appears that the clinical trial cannot be concluded successfully. Members of the DSMB include [name]. (Chair; Professor, Boston University), [name]. (Associate Professor, Massachusetts General Hospital), and [name]. (Assistant Professor, Duke University). These DSMB members have experience serving on other DSMBs and conducting research on severe mental illness and mobile technologies.

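### Two parts of section D3 give conflicting rules on which non-fatal serious adverse events go to the DSMB within 10 days

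*Combined protocol and SAP*

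**What the plan says.** Both rules are current text in section D3 (Data Safety Monitoring Plan), and both concern what the DSMB receives.

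- **Adverse Event Reporting** (in subsection 2) sets timeframes by type of SAE. Item 1: SAEs that are expected and unrelated go to the IRB within 14 days and to the DSMB in bi-annual reports. Item 2: "unexpected or related SAEs" go "to Butler IRB and DSMB within 10 days of ascertainment". Item 3: all deaths go to both bodies within 5 days.
- **Data and Safety Monitoring Board** (subsection 3) says: "Only reports that meet the criteria of being a death (within 5 calendar days) or unexpected and related to study procedures", the latter within 10 calendar days, are reported to the DSMB within the stated time. It adds: "Summary reports of all adverse events will be provided to DSMB in bi-annual reports".

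Three other statements bear on the point. Adverse Event Reporting says that the team anticipates SAEs, naming suicide attempts and readmissions, but that "it is unlikely that SAEs will be related to the study procedures". Adverse Events Definitions describes an expected event as "an event that may be reasonably anticipated to occur as a result of the study procedure and is described in the consent form". It calls an event unexpected if it is both absent from the consent form and unanticipated, or if it proves more serious or more frequent than anticipated.

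**The concern.** One rule joins its two conditions with *or*, the other with *and*, for the same recipient and the same 10-day limit. The second opens with *only*, so it cannot be read as adding to the first. Staff who work from the DSMB subsection would hold back SAEs that Adverse Event Reporting says the board must have within 10 days.

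The board is the body that "will independently make recommendations to the PIs to continue, to amend or to terminate the trial". The event that matters most is one judged related to the intervention. A suicide attempt attributed to the app is a signal the board should see promptly even though suicide attempts are anticipated in this population. Under the DSMB subsection, that event waits for the next periodic report.

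**Working it through.** No power or sample-size figure is involved. The check applies both rules to every class of event and compares the DSMB timing.

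| Event | Adverse Event Reporting | DSMB subsection | Result |
|---|---|---|---|
| Death | 5 days | 5 days | agree |
| Non-fatal SAE, unexpected and related | 10 days | 10 days | agree |
| Non-fatal SAE, expected and unrelated | bi-annual | bi-annual | agree |
| Non-fatal SAE, expected and related | 10 days | bi-annual | **conflict** |
| Non-fatal SAE, unexpected and unrelated | 10 days | bi-annual | **conflict** |

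Adverse Event Reporting expedites three of the four non-fatal classes; the DSMB subsection expedites one.

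**Is the *or* a slip?** No. Items 1 and 2 are exact complements: an SAE that is not both expected and unrelated must be unexpected or related. Changing item 2 to *and* would leave two classes with no timeframe.

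**Which conflicting class matters?** The study's own SAE list is death, suicide attempt and inpatient psychiatric hospitalization. Deaths agree under both rules. The protocol anticipates the other two, so they do not ordinarily meet its definition of unexpected, whatever the consent form says. The unexpected-but-unrelated class is therefore small: events more serious or frequent than anticipated, or SAEs that meet only the general definition, such as a medical admission. The main affected class is an anticipated SAE judged related.

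**How long is the wait?** This assumes that bi-annual means every six months; the protocol does not give the interval in months. The longest wait is 365.25 / 2 = 182.6 days, about 183, against a limit of 10 days. If events fall evenly over the interval, the mean is 182.6 / 2 = 91.3 days, and the share waiting more than 10 days is 1 − 10/182.6 = 0.945.

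**How many events?** The documents give no rates. As illustration only, assume that 10% to 30% of the 20 patients have one non-fatal SAE, all anticipated, and that 5% to 10% of these are judged related. The affected count is N × p × r, from 20 × 0.10 × 0.05 = 0.1 to 20 × 0.30 × 0.10 = 0.6. Neither assumed rate has a source in the protocol, and the textual conflict does not depend on them.

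**The case against.** The best case on the other side is that the conflict is real but nearly empty.

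- **Most events are treated alike.** An anticipated readmission judged unrelated is bi-annual under both rules, and the protocol considers related SAEs unlikely. This stands and limits the practical size.
- **Other safeguards are intact.** Unexpected or related SAEs still reach the IRB within 10 days, the principal investigators are contacted immediately, and section D1 sends intervention-related events to the full IRB committee. This stands. A reader might infer that safety reporting as a whole is deficient, but the documents do not support that.
- **A later document may settle it.** The principal investigators and the DSMB Chair are to write a Data Safety Monitoring Plan for the board's approval. That may help, but it would be drafted from a protocol that gives two answers, and nothing in the protocol says which rule governs.

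A reader might also infer that, because the consent form is not available, suicide attempts and readmissions could all count as unexpected, so that most SAEs in the trial would be caught in the conflict. The definitions do not support this: an event must be unanticipated as well as undescribed, unless it exceeds what was anticipated, and the protocol says these events are anticipated. The definition of expected is narrower, requiring mention in the consent form, so the two definitions leave a gap between them. Falling into that gap does not make an ordinary relapse unexpected.

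**Conclusion.** The inconsistency is certain from the text: two of four non-fatal SAE classes get different DSMB rules, and nothing in the protocol reconciles them. It should be corrected.

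Its practical size is small. It falls mainly on anticipated SAEs judged related to the app, and few are likely; no firm count can be given without event rates. For such an event the difference is 10 days against as much as about 183, if the periodic reports are six-monthly. The consequence is confined to DSMB oversight and does not touch the trial's descriptive analysis.

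**What to change.** Replace the restrictive sentence in the DSMB subsection with:

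> Deaths (within 5 calendar days), SAEs that are unexpected or related to the intervention or study procedures (within 10 calendar days), and non-serious events that are unexpected and related to study procedures (within 10 calendar days) will be reported to the DSMB; all other events will be in the bi-annual reports.

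Three details matter. The existing sentence is not limited to serious events, so changing only *and* to *or* would also expedite non-serious events that are merely unexpected or merely related. Restricting it to SAEs would lose early reporting of non-serious events that are both; the third clause keeps it. Naming both intervention and study procedures removes a second ambiguity, since the attribution scale refers to the intervention and the DSMB sentence to study procedures.

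The cost is one sentence and at most a few more expedited reports, using the adverse event form already completed for the IRB. Expected and unrelated readmissions stay in the bi-annual report.
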